### **7.2.2. Adverse Events**

MedDRA version 22.0 (or higher) will be used to map reported AEs to MedDRA terms. The MedDRA LLT will be used in the treatment-emergent computation. PTs identified as clinically identical or synonymous may be grouped together under a single consolidated PT. For example, 'Neutropenia' and 'Neutrophil count decreased' may be aggregated and reported as 'Neutropenia.' The NCI CTCAE version 5.0 will serve as the reference document for grading the severity of all AEs and other symptoms.

Preexisting conditions are defined as AEs that begin prior to the first dose of study treatment.

A TEAE is defined as any AE that begins between the day of first dose and 30 days after treatment discontinuation (or up to any time if serious and related to study treatment), or any preexisting condition that increases in CTCAE grade between the day of first dose and 30 days after treatment discontinuation (or up to any time if serious and related to study treatment).

Comparisons of preexisting conditions to on-treatment events at the LLT level will be used in the treatment-emergent computation.

An SAE is any AE during this study that results in one of the following outcomes: death, initial or prolonged inpatient hospitalization, a life-threatening experience (that is, immediate risk of dying), persistent or significant disability/incapacity, congenital anomaly/birth defect, or considered significant by the investigator for any other reason. Additionally, important medical events that may not result in death, be life-threatening, or require hospitalization may be

considered SAEs when, based on appropriate medical judgment, they may jeopardize the patient and may require medical or surgical intervention to prevent 1 of the outcomes listed in this definition.

The following summaries and listings will be produced:

- overview of AEs
- summary of TEAEs by PT (any grade and Grade  $\geq 3$ )\*
- summary of TEAEs by System Organ Class and PT (any grade and Grade  $\geq 3$ )\*
- summary of TEAEs by PT and maximum grade (1 through 5)\*
- summary of SAEs by PT (any grade and Grade  $\geq 3$ )\*
- summary of TEAEs as reason for study treatment discontinuation by PT (overall and for each study treatment)
- summary of TEAEs leading to dose adjustments by PT (overall and for each study treatment)
- listing of SAEs, and
- listing of DLTs.

Summaries marked with an (\*) will be produced both using all TEAEs/SAEs and using only TEAEs/SAEs related to study treatment, as assessed by the investigator (yes or no).

### **7.2.3. Deaths**

A summary table of all deaths, including reasons for deaths, will be provided. For deaths due to AE, the PT will be provided. In addition to the tabular summary, a by-patient listing of all deaths on study not attributed to study disease by the investigator will be provided.

### **7.2.4. Clinical Laboratory Evaluation**

All relevant hematology and chemistry laboratory values will be graded according to CTCAE version 5.0. These calculated grades will be summarized by cycle and maximum postbaseline grade over the entire study for each treatment arm/cohort. Treatment-emergent changes will be summarized by the maximum postbaseline grade, and a shift table of baseline grade by maximum postbaseline grade will be produced.

### **7.2.5. Vital Signs and Other Physical Findings**

Temperature, blood pressure, pulse rate, weight, BSA, and Lansky/Karnofsky Performance Status will be summarized by cycle, including a summary of treatment-emergent abnormal changes.

### 7.2.6. *Electrocardiograms*

ECGs are scheduled to be performed. A listing of ECG findings at baseline and unscheduled postbaseline visits that are considered to be a medical history condition or an AE will be provided. Other analyses may also be done as appropriate.

## 7.3. **Efficacy Analyses**

Unless otherwise noted, all efficacy analyses will be performed on the treated population and summarized by cohort where appropriate. Additionally, all patients assigned to the RP2D (for example, the applicable cohort from dose escalation and the dose expansion cohort) within each study part may be aggregated and summarized together.

### 7.3.1. *Primary Efficacy Endpoints*

The study was not designed to make an efficacy assessment in Parts A and B, while ORR will be assessed as co-primary endpoint in Part C if a RP2D is achieved. In Part C, ORR is the percentage of patients with a BOR  $\geq$  PR (CR, PR, and MR) per INRC (Park et al. 2017). The response criteria integrate the responses of all lesions using computed tomography/magnetic resonance imaging and/or MIBG/fluorodeoxyglucose-positron emission tomography lesions, and assessment of bone marrow disease. Details are provided in Protocol Section 9.4.6.2.1. All time point responses observed while on study treatment and during short-term follow-up, but before the initiation of post-discontinuation therapy, will be included in the derivation. The primary analysis of response will be based on confirmed responses as defined in [Table JPCS.7.2](#). However, summaries including unconfirmed responses will also be provided. For the interim analysis for Part C, unconfirmed responses may be used.

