Radiologic imaging	X	RECIST v1.1 should be used for all non-CNS tumors; RANO should be used for CNS tumors. For patients with non-CNS tumors, perform a CT scan of the known lesion(s) and of the chest. For CNS tumors, perform MRI of the primary lesion including the entire brain or spine as applicable. For brain lesions, also include MRI of the spine if history of drop metastases or if new drop metastases were present at baseline scan. Imaging is not required if participant has discontinued due to progressive disease. For patients who discontinued for any reason other than progressive disease, scans should continue per the on-treatment schedule for radiologic imaging. Imaging facility, image acquisition protocol, and imaging modality should be consistent for all visits for a given patient.
Lumbar puncture	X	Assess CSF cytology and tumor markers (alpha-fetoprotein and beta-HCG) according to institutional/standard guidelines for applicable patients who had positive tumor markers or cytology at baseline and who are off study treatment for reasons other than disease progression.
Hematology	X	See Section 10.2, Appendix 2.
Clinical chemistry	X	Include liver function tests. See Section 10.2, Appendix 2.
Collection of poststudy anticancer treatment	X	Telephone assessment is acceptable. For all patients, details on subsequent anticancer treatment (start/stop dates and treatments administered).

Abbreviations: BSA = body surface area; CTCAE = Common Terminology Criteria for Adverse Events, CCI

RANO = Response Assessment in Neuro-Oncology; RECIST = Response Evaluation Criteria in Solid Tumors.

^a Short-term follow-up begins when the patient and investigator agree that the patient will no longer continue study treatment and lasts approximately 30 days from the last administration of study drugs.

Continued Access Schedule of Activities for Parts A and B

Parts A and B			
Visit	Study Treatment	Follow-Up	Notes
	501-5XX	901	
Procedure			
AE collection/CTCAE grading	X	X	Per CTCAE Version 5.0. Collect all AEs/SAEs. Per standard of care, monitor vital signs and perform standard laboratory tests (hematology, chemistry, and pregnancy testing). See Sections 6.7.1.1 and Section 10.2 , Appendix 2.
Administer abemaciclib	X		See Section 6.1 .
Administer temozolomide (if applicable)	X		Administer Days 1-5 of each cycle. Continuation on chemotherapy beyond Cycle 12 will be up to the investigator's discretion and the individual patient's situation. See Section 6.1 .

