Tumor evaluation: CT or MRI		End of Cycles 2, 4, and 6, then at the end every 4th cycle	
 Up to 1 week prior to the start of the next planned cycle of therapy Repeat assessment ≥4 weeks after initial response for patients with complete response, partial response, and minor response Use same modality throughout the study Scans will be performed and reviewed locally
Tumor evaluation: MIBG or PET CT		End of Cycles 2, 4, and 6, then at the end every 4th cycle	
 Up to 1 week prior to the start of the next planned cycle of therapy PET CT only for patients with non-MIBG avid lesions Repeat assessment ≥4 weeks after initial response for patients with complete response, partial response, and minor response Scans will be performed and reviewed locally
Bilateral bone marrow aspirates/biopsies		End of Cycles 2, 4, 6 and then after every 4th cycle - only for patients with marrow disease and all patients (even if no marrow disease) following Cycle 6	Up to 1 week prior to the start of the next planned cycle of therapy
Biomarkers – plasma	X	X	
 Collect pre-dose at C1D1 on participants CCI only Collect at disease progression and/or study discontinuation on participants CCI
Biomarkers - whole blood	X		
 For participants CCI whole blood dried blood spot For participants CCI whole blood sample If not collected during screening/baseline, then obtain at C1D1 If blood volume restrictions prevent collection during screening/baseline and C1D1, then sample can be collected at a subsequent timepoint

Part C			
Procedures	During Cycle 1	Cycle 2 onward	Instructions
			
 Only one sample is needed per patient See Section 8.8
Drug product acceptability and palatability questionnaire	Days 1 and 15	Cycle 2 Day 1 only	
 For patients \leq5 years old, only the caregiver will complete For patients \geq6 to $<$12 years old, patient and caregiver will complete For patients \geq12 years old, only the patient will complete Perform at time of dosing or within approximately 30 minutes after dose If method of abemaciclib administration or formulation (tablets to granules or vice versa) changes, the appropriate questionnaire corresponding to the new administration method and formulation should be completed at the clinic visit following this change

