Relative Day within Cycle	Begins when the patient and the investigator agree that the patient will no longer continue study treatment and lasts approximately 30 days.	Begins when short-term follow-up period is complete and continues until death, study withdrawal, or the patient is lost to follow-up. In all cases, no follow-up procedures will be performed for a patient who withdraws consent/assent unless he or she has explicitly provided permission and consent/assent.	
Clinically directed physical examination	X		Evaluations per examiner's discretion and patients' symptoms
Vital signs	X		Includes height, weight, blood pressure, pulse, temperature, and respiratory rate
Performance status	X		
 • Lansky for age <16 years • Karnofsky for age ≥16 years For patients who turn 16 years old while on study, Karnofsky should be used after the 16 th birthday

CCI

Part C			
	Short-Term Follow-Up (30±7 Days)	Long-Term Follow-Up (90±14 Days)	Comments
Visit	801	802-X	
Relative Day within Cycle	Begins when the patient and the investigator agree that the patient will no longer continue study treatment and lasts approximately 30 days.	Begins when short-term follow-up period is complete and continues until death, study withdrawal, or the patient is lost to follow-up. In all cases, no follow-up procedures will be performed for a patient who withdraws consent/assent unless he or she has explicitly provided permission and consent/assent.	
Tumor restaging evaluation CT or MRI and MIBG or PET CT	X	X	
 • Use same modality throughout the study • PET CT only for patients with non-MIBG avid lesions • Not required if PD is documented while on treatment, or if staging has been performed within the past 3 weeks • Perform during every long-term follow-up visit if PD has not occurred • Scans will be performed and reviewed locally
Adverse events collection/CTCAE grading	X	X	
 • CTCAE Version 5.0 • After Visit 801, only study treatment-related serious events are reported
Concomitant medication	X		
Hematology	X		
 • Local testing • See Section 10.2, Appendix 2
Clinical chemistry	X		
 • Local testing • See Section 10.2, Appendix 2

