In Part C only, patients will undergo a ¹²³I-MIBG scan for the presence or absence of MIBG avid lesions at the start of therapy and according to the SoA (Section 1.3.2). Those with MIBG avid lesions will be evaluable for MIBG response. For all patients with MIBG-avid lesions, including those with disease also detectable by CT/MRI, serial MIBG evaluations are required per the SoA. PET-CT may replace MIBG only for patients without MIBG avid lesions.

In Part C only, response confirmation is required based on a repeat assessment completed at least 4 weeks after initial response for patients with complete response, partial response, and minor response.

See Section 9.4.6 for definitions of the efficacy endpoints.

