Bone marrow response is determined by cytology (recommended to be accompanied by immunocytoLOGY)/histology (accompanied by immunohistochemistry [Burchill et al. 2017]). Use the bone marrow sample with the highest percentage of tumor infiltration to assess response.

Grading is as follows:

- **Complete Marrow Response**: No tumor infiltration on reassessment, independent of baseline tumor involvement
- **Progressive Marrow Disease**: either
 - bone marrow without tumor infiltration that becomes $> 5\%$ tumor infiltration on reassessment, or

- bone marrow with tumor infiltration that increases by >2 times and has >20% tumor infiltration on reassessment
- **Minimal Disease (MD):** any of the following:
 - $\leq 5\%$ tumor infiltration at baseline and remains > 0 to $\leq 5\%$ tumor infiltration on reassessment, or
 - no tumor infiltration at baseline and $\leq 5\%$ tumor infiltration on reassessment, or
 - $> 20\%$ tumor infiltration at baseline and > 0 to $\leq 5\%$ tumor infiltration on reassessment
- **Stable Marrow Disease:** Persistence of $> 5\%$ tumor infiltration on reassessment that does not meet the criteria for CR, MD, or PD.

Overall response is as follows:

- **Complete Response (CR):** All components meet criteria for CR
- **Partial Response (PR):**
 - PR in ≥ 1 component AND
 - ALL other components are either CR, MD (bone marrow only), PR (soft tissue or bone), or NI (site not involved at study entry remain uninvolved) AND
 - No component with PD
- **Minor Response (MR):**
 - PR or CR in ≥ 1 component AND
 - SD in ≥ 1 component AND
 - No component with PD
- **Stable disease (SD):**
 - SD in ≥ 1 component AND
 - No better than SD or NI (site not involved at study entry and remains uninvolved) AND
 - No component with PD
- **Progressive Disease (PD):** Any component with PD

The overall response based on the combined evaluations is summarized in the table below. The best response observed at any time point for each individual patient will be considered that patient's best overall response on this study.

Primary tumor	Soft tissue or bone metastatic disease	Bone marrow metastatic disease	Overall response
CR	CR	CR	CR
CR for one category and CR or NI for remaining categories			CR
CR	CR	MD	PR
CR	PR	CR	PR
CR	PR	MD	PR
CR	PR	NI	PR
CR	NI	MD	PR
PR	CR	CR	PR
PR	CR	NI	PR
PR	CR	MD	PR

Primary tumor	Soft tissue or bone metastatic disease	Bone marrow metastatic disease	Overall response
PR	PR	CR	PR
PR	PR	NI	PR
PR	PR	MD	PR
PR	NI	CR	PR
PR	NI	NI	PR
PR	NI	MD	PR

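### A Part C response first seen at Visit 801 enters the primary ORR derivation, but no admissible scheduled scan can confirm it

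*SAP*

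**What the plan says.** **Admissible time points.** SAP 7.3.1 (primary ORR) and SAP 7.3.2.2 (best overall response, Part C) use "All time point responses observed while on study treatment and during short-term follow-up, but before the initiation of post-discontinuation therapy".

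**Confirmation.** SAP 7.3.1 states: "The primary analysis of response will be based on confirmed responses as defined in" Table JPCS.7.2. That table requires the second assessment at least 28 days after the first. Protocol 8.1 agrees: "response confirmation is required based on a repeat assessment completed at least 4 weeks after initial response". The Part C on-treatment schedule repeats the instruction: "Repeat assessment ≥4 weeks after initial response for patients with complete response, partial response, and minor response".

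**What happens without confirmation.** In Table JPCS.7.2 a second assessment before 28 days gives SD. A missing or non-evaluable second assessment gives SD if the response came after study day 35, and NE otherwise.

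**Scans after treatment.** The Part C post-treatment schedule (protocol 1.3.2) has Visit 801 at 30±7 days and long-term visits at 90±14 days. Both include CT or MRI with MIBG or PET. Of the long-term visits it says: "Perform during every long-term follow-up visit if PD has not occurred". Staging is waived if PD was documented on treatment or if staging was done in the previous 3 weeks.

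**The protocol's own definition.** Protocol 9.4.6.2.1 describes best overall response as "The best response observed at any time point for each individual patient", with neither a follow-up cut-off nor a confirmation rule in that sentence.

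**The concern.** The SAP opens the window wide enough to admit a response at Visit 801 and closes it before the confirmation that it demands can take place. However durable the response, and even with no new therapy, the patient is a non-responder in the primary analysis. The scan that could settle the matter is scheduled and collected, then left out.

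Stopping treatment without PD is built into Part C: under protocol 6.6, having to discontinue any one study drug ends all protocol therapy, apart from the allowance for chemotherapy after Cycle 12. Some patients will therefore reach Visit 801 free of progression and untreated. The error runs one way, against the combination, on a co-primary endpoint. The two documents can also classify the same patient differently.

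**Working it through.** **Inputs.** Visit 801 at 30±7 days, long-term visits at 90±14 days, and on-treatment scans up to 7 days before the next planned cycle (protocol 1.3.2). Confirmation at 28 days or more, and the study-day-35 footnote (SAP Table JPCS.7.2). 46 patients at the RP2D (SAP 6.3). Day 0 is the decision to stop treatment, when the Part C schedule starts short-term follow-up.

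**Step 1. Windows.**
- Visit 801: 30−7 to 30+7 = day 23 to 37, which is 15 allowed days.
- Long-term interval: 90−14 to 90+14 = 76 to 104 days.

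**Step 2. Response first seen at Visit 801.**
- Earliest confirming date: 23+28 = day 51, up to 37+28 = day 65.
- The admissible period ends at about day 37, so no admissible scan can confirm it.
- The first long-term scan would meet the interval. Counted from Visit 801 it is at least 76 days later. Counted from day 0, the shortest gap is 76−37 = 39 days. Both exceed 28.

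**Step 3. Response first seen on an earlier scan within short-term follow-up.** The latest confirmable day is 37−28 = day 9. After that, the case is the same as Step 2. The 3-week waiver can also remove the Visit 801 scan for such a patient.

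**Step 4. Response first seen at the last on-treatment scan.** Let that scan be L days before the stop. The gap to Visit 801 is then 23+L to 37+L days.

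| L (days) | Gap (days) | Visit 801 days, of 15, with gap ≥28 |
|---|---|---|
| 0 | 23–37 | 10 |
| 1 | 24–38 | 11 |
| 2 | 25–39 | 12 |
| 3 | 26–40 | 13 |
| 4 | 27–41 | 14 |
| 5–7 | 28–44 | 15 |

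This response can normally be confirmed. With L = 0 it is at risk only if Visit 801 falls on day 23 to 27 and no later repeat is done by day 37.

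**Step 5. SD or NE.**
- Cycle 3 Day 1 is study day 2×21+1 = 43, so the first scheduled scan falls on study day 36 to 43. A response on schedule that goes unconfirmed therefore becomes SD.
- NE needs a response by study day 35. At Visit 801 that means stopping by study day 35−23 = 12.
- In both cases the patient is a non-responder.

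**Step 6. Size.**
- One patient is 1/46 = 2.2 percentage points.
- The plan's figure of 46 cannot be verified, because the null and alternative response rates and the boundaries are redacted. An exact search for Simon's optimal design (one-sided 0.025, power 80%) returns 46 for more than one assumed pair: 0.42 versus 0.65 (5/11, 25/46; alpha 0.0246, power 0.802) and 0.40 versus 0.63 (7/15, 24/46; alpha 0.0247, power 0.808). The published 46 does not identify the design.
- Neither document says how many first responses occur at Visit 801.

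**The case against.** **Responses at the end of treatment.** A reader might infer that any response found as treatment ends is lost. The documents do not support that. Part C has no separate end-of-treatment visit, Visit 801 lies inside the SAP window, and Step 4 shows that it usually meets 28 days. Protocol 8.1 also obliges the site to repeat the assessment at 4 weeks or later. It follows that patients who stop for toxicity while already responding are mostly safe. The gap concerns patients with no response at any on-treatment scan who first respond about a month after stopping. This objection stands and limits the point.

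**Power.** A reader might assume response rates and a share of lost responders and read off a fall in power. Both inputs would be guesses. The interim need not be affected either, because SAP 7.3.1 allows unconfirmed responses there. This stands.

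**Mitigation.** SAP 7.3.1 promises that "summaries including unconfirmed responses will also be provided". The affected patients will be visible, but the primary estimate and its test will not change.

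**A conservative cut is legitimate.** Limiting response to treatment plus about 30 days is defensible in a single-arm trial. But responses after new therapy are already excluded, so closing the confirmation window at Visit 801 adds no protection against later treatment.

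**The protocol sentence is not a full algorithm.** This is true, and protocol 9.4.1 refers to the SAP for detail. The two texts still differ and should be aligned.

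**Parts A and B.** SAP 7.3.2.1 uses the same window, and there "scans should continue per the on-treatment schedule for radiologic imaging" after a stop for reasons other than PD. A reader might extend the point to them. They have no formal efficacy assessment, and the SAP allows unconfirmed responses for their endpoints, so little turns on it.

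**Conclusion.** The point holds in a narrow form. In Part C, a response first seen at Visit 801, or after about day 9 of short-term follow-up, is admitted to the derivation but has no admissible scheduled scan to confirm it. It becomes SD or NE and lowers the primary ORR, although the protocol collects the scan that could confirm it. A response first seen on the day treatment stops is exposed only when Visit 801 falls on day 23 to 27 without a later repeat.

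The bias is downward and probably small. Each affected patient costs 2.2 points of ORR (1/46). The number affected and the effect on power cannot be derived from the documents. The conclusion assumes that the admissible period ends with the Visit 801 window at day 37, and that no unscheduled scan or new therapy intervenes.

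**What to change.** **SAP 7.3.1 and 7.3.2.2.** State that a response first seen by the end of short-term follow-up may be confirmed by any later assessment at least 28 days after it, long-term follow-up scans included, provided that assessment precedes PD, new anticancer therapy and the data cut-off.

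**Protocol 9.4.6.2.1.** Give the best-overall-response sentence the same window and the confirmation rule.

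**Reporting.** List the responses confirmed after treatment stopped.

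**Cost and limits.** The change is to wording, and the imaging is already scheduled. A few responses will be confirmed off treatment, which the listing makes plain. Two limits remain:
- The INRC table returns a not-done result when an involved category is not assessed. No bone marrow row is visible in the public Part C post-treatment schedule (one row is redacted). Patients with marrow disease may therefore stay unconfirmed unless marrow is reassessed.
- Protocol 9.4.6.2 sets the primary analysis 6 cycles (6×21 = 126 days) after the last patient enters treatment, so some late enrollees' long-term scans may fall after the cut-off.

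Make the change before the primary analysis of Part C.

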9.4.6.2. Part C Efficacy Analyses

In Part C, the primary efficacy measure is investigator-assessed tumor response as defined by INRC. The primary endpoint ORR will be based on the 2017 INRC (Park et al. 2017) as described in Section 9.4.6.2.1. The primary analysis of ORR will occur 6 cycles after last patient has entered treatment, in order to ensure adequate response and durability of response data is available at the time of analysis. The point estimate of ORR with a two-side exact 95% confidence interval will be provided, and one-sided exact p-value will be reported.

9.4.6.2.1. 2017 INRC

For Part C, efficacy will be evaluated using the 2017 INRC (Park et al. 2017).

A responder is defined as any patient who exhibits a CR, PR, or MR.

The response criteria integrate the response of all lesions using CT/MRI and/or MIBG/FDG-PET lesions, and assessment of bone marrow disease.

Primary tumor (soft tissue) response is as follows:

- **Complete Response (CR):**
 - <10 mm residual soft tissue at primary site AND
 - complete resolution of MIBG-avid tumors or FDG-PET uptake (for MIBG-nonavid tumors) at primary site
- **Partial Response (PR):**
 - ≥30% decrease in longest diameter of primary site AND
 - MIBG-avid tumors or FDG-PET uptake (for MIBG-nonavid tumors) at primary site is stable, improved, or resolved
- **Stable Disease (SD):** Neither PR nor PD at the primary site
- **Progressive Disease (PD):**
 - >20% increase in longest diameter taking as reference the smallest sum while on study, including baseline sum if that is the smallest, AND
 - minimum absolute increase of 5mm in longest dimension
 - Note: a lesion that does not meet PD measurement criteria but has fluctuating MIBG avidity will not be considered PD

Soft tissue and bone metastatic disease tumor response is as follows:

- **Complete Response (CR):** Complete resolution of all disease sites defined as:
 - nonprimary target and nontarget lesions <10 mm AND
 - lymph nodes identified as target lesions decrease to a short axis <10 mm AND
 - MIBG-avid update or FDG-PET uptake (for MIBG-nonavid tumors) of nonprimary lesions resolves completely
- **Partial Response (PR):** ≥30% decrease in sum of diameters^a of nonprimary target lesions compared with baseline AND all of the following:

- Nontarget lesions may be stable or smaller in size AND

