#### 7.3.2.2. Part C

**BOR:** defined per INRC (Park et al. 2017). Details are provided in Protocol Section 9.4.6.2.1. All time point responses observed while on study treatment and during short-term follow-up, but before the initiation of post-discontinuation therapy, will be included in the derivation. Responses will require confirmation ([Table JPCS.7.2](#)), but where appropriate BOR and endpoints using BOR may also consider unconfirmed responses (for example, interim analysis).

**DoR:** defined only for responders (patients with a CR or MR or PR). It is measured from the date of first evidence of a CR or MR or PR to the date of objective progression or the date of death due to any cause, whichever is earlier.

**DCR:** the percentage of patients with a BOR of CR, MR, PR, or SD.

**CBR:** the percentage of patients with a BOR of CR, MR, PR, or SD for at least 6 months.

**Investigator assessed PFS:** the time from first dose of any drug in study treatment to documented disease progression per INRC or death, whichever occurs first. The Kaplan-Meier method (Kaplan and Meier 1958) will be used to estimate the PFS curves as well as PFS rates at appropriate time intervals (for example, at 3 and 6 months). Detailed censoring rules are provided in Table JPCS.7.3.

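### SAP Table JPCS.7.2 is not monotone: in Part C, PR followed by MR is scored SD, while MR followed by MR at 28 days or more is a confirmed response

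*SAP*

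**What the plan says.** SAP 7.3.1 defines the Part C ORR by a best overall response of at least "PR (CR, PR, and MR) per INRC". Protocol 9.4.6.2.1 agrees on the categories: "A responder is defined as any patient who exhibits a CR, PR, or MR".

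On confirmation, SAP 7.3.1 says: "The primary analysis of response will be based on confirmed responses as defined in" Table JPCS.7.2. The rows that matter here are:

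- MR, then MR or better at 28 days or more: confirmed MR.
- PR, then PR or better at 28 days or more: confirmed PR.
- CR, then CR at 28 days or more: confirmed CR.
- CR then PR, CR then MR, and PR then MR: SD. These three rows carry no interval condition.

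On which assessments enter, the SAP says: "All time point responses observed while on study treatment and during short-term follow-up", up to the start of any later therapy. It does not say how a patient with three or more assessments is handled. Protocol 8.1 says: "response confirmation is required based on a repeat assessment completed at least 4 weeks after initial response". It does not say which category the repeat must show.

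Summaries that include unconfirmed responses are also planned, and the Part C interim analysis may use them.

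**The concern.** A confirmation rule should never rank a patient lower for having done as well or better at every visit. This table does. PR then MR is at least as good at both visits as MR then MR, yet the first patient is SD and the second is a responder.

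Requiring the later assessment to match or beat the first explains why a falling patient is not given a confirmed CR or PR. It does not explain withholding a confirmed MR from someone who was at least MR twice, 28 days or more apart.

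At stake is the count compared with the Simon threshold. Under SAP 7.3.2.2, DoR is defined only for responders, so a patient scored SD leaves that analysis as well.

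**Working it through.** **Inputs**

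- Response categories: SAP 7.3.1 and Protocol 9.4.6.2.1.
- Confirmation rows: SAP Table JPCS.7.2.
- Scan schedule: "End of Cycles 2, 4, and 6, then at the end every 4th cycle" (Protocol 1.3.2). With 21-day cycles and no delay, the first three scans fall at days 2 × 21 = 42, 4 × 21 = 84 and 6 × 21 = 126.
- Scan window: up to 1 week before the next cycle (Protocol 1.3.2). A cycle may start 1 day early (Protocol 6.1.3).
- Analysis time: "The primary analysis of ORR will occur 6 cycles after last patient has entered treatment" (Protocol 9.4.6.2), about day 126 for that patient.
- 46 patients at the RP2D (SAP 6.3). This figure cannot be reproduced because the null and alternative ORR are redacted. The check does not depend on it.

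**Step 1: all ordered pairs, 28 days or more apart**

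| First \ second | CR | PR | MR |
|---|---|---|---|
| CR | CR | SD | SD |
| PR | PR | PR | SD |
| MR | MR | MR | MR |

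Six of 9 pairs are responders and 3 are SD. Reading down the MR column, a better first assessment turns a responder into a non-responder. The same happens in the PR column for CR then PR, compared with PR then PR.

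**Step 2: does the 28-day interval decide this?** Not at scheduled scans through Cycle 6. The smallest gap is 2 × 21 − 7 = 35 days, or 2 × 20 − 7 = 33 days with two early starts. Both exceed 28, so the category rows decide.

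**Step 3: do later assessments rescue these patients?** Take the most lenient reading: every pair is searched, and a pair confirms if the gap is at least 28 days and the second category is the same or better.

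- Days 84/126 (gap 42): 3 of 9 sequences are SD.
- Days 42/84/126 (gaps 42, 42, 84): only CR-PR-MR fails, 1 of 27.
- Days 84/112/126 (gaps 28, 14, 42), with an extra repeat scan at day 112: a sequence fails when both later results fall below the first. A first CR gives 2 × 2 = 4 and a first PR gives 1, so 5 of 27. PR-MR-MR is one of them, because its two MRs are only 14 days apart.

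If instead only the first response and the next assessment were compared, 3 × 3 = 9 of 27 sequences at days 42/84/126 would be SD. The SAP does not say which reading applies.

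If any two responses at least 28 days apart confirmed at the lesser category, the three all-pairs counts would be 0 of 9, 0 of 27 and 0 of 27.

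**Step 4: can these sequences occur without PD?** Under Protocol 9.4.6.2.1, yes for two of them.

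- PR to MR: primary PR, metastatic CR, marrow not involved is PR overall. Primary SD with the same other components is MR overall. PR needs a decrease of at least 30%, so at most 0.70 of baseline length. From a nadir of 0.70, PD needs more than 0.70 × 1.20 = 0.84. A primary tumour between 0.70 and 0.84 of baseline is SD and not PD.
- CR to PR: CR in primary and metastatic sites with minimal marrow disease is PR overall. Minimal disease includes marrow clear at baseline with up to 5% infiltration later. Patients without marrow disease are re-examined after Cycle 6, so a CR at Cycle 4 can become PR then.

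**The case against.** The best defence is that the table applies one principle: the later assessment must sustain the initial category. Overall PR allows no stable component and MR requires one, so a move from PR to MR means that some component lost its response. Not confirming that is conservative, and the rule was fixed before Part C enrolment (SAP 4). This stands as a reason to withhold a confirmed PR. It does not reach the MR, which was met or exceeded twice.

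The counts also treat every sequence as equally reachable. That criticism stands. Marrow that was clear and rises above 5% is PD. A primary tumour below 10 mm that grows by 5 mm or more is PD too. To be SD without PD it must stay under 15 mm with less than a 30% decrease, which needs a baseline below 15 / 0.70 ≈ 21 mm. Falls from CR to MR are therefore hard to reach. The most plausible case is PR to MR in multi-component disease. The counts describe patterns, not patient frequencies.

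Only the last patients are cut off near day 126. Others have later scans, and a later MR at least 28 days after the first MR confirms. The scheduled day-126 scan can itself serve as the repeat assessment, so a day-112 scan need not exist. This limits the number affected but does not remove it.

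A reader might infer that the table contradicts the SAP's own DoR definition: "It is measured from the date of first evidence of a CR or MR or PR to the date of objective progression" or death. It does not. That definition says how long an established response lasts, not how one is confirmed. A reader might also infer a conflict with Protocol 8.1. There is none, because that section is silent on the category of the repeat.

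**Conclusion.** The point holds as an internal flaw in the confirmation rule that governs the primary Part C ORR. Followed exactly, the table scores some patients SD who were in response at both visits, 28 days or more apart. Under the most lenient search, those left unrescued are patients with only two response assessments, the second shallower, patients whose category falls at every assessment, and some with an added repeat scan less than 28 days before the next.

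The rule can only lower ORR, so it does not inflate type I error. A reader might infer a stated loss of power. The documents do not support one: the null and alternative ORR are redacted, the affected share is not given, and there is no loss against plan if the alternative was set on this same table. One patient is 1/46 = 2.2 points of ORR, but that is the weight of any single patient and does not measure this rule. The planned unconfirmed-response summaries would show these patients, and SAP 7.3.2.2 lets endpoints built on BOR consider unconfirmed responses. Neither changes the primary count.

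The day counts assume 21-day cycles without delay. The flaw should be fixed, but it does not undermine the design.

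**What to change.** If no aggregate Part C response data have been reviewed, including by the DMC:

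- Amend three rows of Table JPCS.7.2 so that two responses at least 28 days apart confirm at the lesser category: PR then MR = MR, CR then MR = MR, CR then PR = PR. Keep SD under 28 days.
- State in one sentence that all pairs of time points are searched.
- Check that the redacted null and alternative ORR were set on a compatible response definition. If the null was set on the current table, the more lenient rule could raise type I error.
- Report ORR under the current table as a sensitivity analysis.

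If such data have been reviewed, keep the current table as primary. Report the revised rule as a sensitivity analysis, labelled as added after data review and not as pre-specified.

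In either case, correct the ORR sentence in SAP 7.3.1. It sets the threshold at PR but lists MR, and should read: BOR of CR, PR or MR.

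The cost is three table rows, one sentence, one phrase and one extra ORR table, with no added patients or data. The drawback is that the revised rule can only add responders in an open-label, single-arm, investigator-assessed trial. That is why the timing condition matters.
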